#### 4.2.1 PRIMARY ENDPOINT

B-lines  $\leq 15$  at the conclusion of ED AHF management (i.e. patient has left the ED) or maximum of 6 hours after enrollment, whichever comes first.

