## 5 STUDY ENROLLMENT AND WITHDRAWAL

### 5.1 PARTICIPANT INCLUSION CRITERIA

- 1) Age  $\geq 21$  years
- 2) Presents with shortness of breath at rest or with minimal exertion
- 3) Clinical diagnosis of AHF and presence of > 15 total bilateral B-lines distributed in at least 4 zones on initial LUS
- 4) Hx of chronic HF and any one of the following:
  - i. Chest radiograph consistent with AHF
  - ii. Jugular venous distension
  - iii. Pulmonary rales on auscultation
  - iv. Lower extremity edema

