### 10.4.3 ANALYSIS OF THE PRIMARY EFFICACY ENDPOINT(S)

The comparison of binary endpoints (B-lines < 15) will be performed using Chi-square or Fishers exact test, as appropriate.

Potential covariates will also be considered in a logistic regression setting to improve precision, which includes baseline co-morbidities, baseline medications (in particular guideline recommended therapies) in-hospital medications, baseline renal function, serum sodium, natriuretic peptide levels, troponin levels, renal function, baseline blood pressure, and discharge medications. Variables such as physical exam, other vital signs, and hemoconcentration may also be included. For NT-proBNP, a percent change greater than 30% and its association with the primary endpoint will be analyzed. This is based on previous work suggesting a 30% change was a key discriminatory threshold for mortality. For hemoconcentration, any increase in value in both hematocrit and hemoglobin during hospitalization will be considered positive. These covariates are known markers of risk and are standard of care assessments for the vast majority of AHF admissions. Covariates with univariately significant association with the outcome will be included together with the treatment indicator in a logistic regression model. Due to limited sample size, we will limit the number of covariates (including treatment indicator) such that there is 10 events per covariate.

---

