### 10.4.4 ANALYSIS OF THE EXPLORATORY ENDPOINT(S)

*DAOOH*: Will be compared using T test or Wilcoxon rank-sum test, as appropriate.

If the distribution of 30 or 90 days *DAOOH* is skewed, the T test may not perform satisfactorily. An alternative approach to evaluate the robustness of the analysis, is to treat *DAOOH* as an ordinal outcome and use the proportional odds (PO) regression model to compare the two arms. The PO model is a generalization of the Wilcoxon (Mann-Whitney) test to estimate the shift in the underlying distribution of *DAOOH* by the intervention. The PO regression allows for adjustment of baseline covariates to enhance power.

We will examine the distribution of B-lines measurements for the groups with and without events separately. Both absolute number and relative change will be evaluated. Receiver Operating Characteristic (ROC) curves will be plotted together with area under the curve (AUC) calculated to understand the prediction performance of the B-line measurements. Sensitivity, specificity, positive and negative predictive values will be computed at a number of thresholds of B-line measurements to understand the trade-off between false positive and false negative. Confidence intervals of statistical measures will be constructed using the bootstrap method. Although 15 B-lines have been previously identified as a valid threshold, an alternative number may be more useful in the ED setting.

For reproducibility analysis, generalized linear mixed-effects models will be fitted to estimate the inter- and intra-observer variability, where both patients and observers are treated as random effects.

We will compare parameters used to identify congestion. This will include a comparison between B-lines measurements and other markers, such as physical exam, NTproBNP, eGFR, and hemoglobin/hematocrit. Bootstrap method will be used for the comparison to account for correlations between the markers and the B-line measurements. We will consider two strategies to explore potential multivariate models:

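### The primary chi-square is valid but uses neither the T00 B-line count nor site; the supplementary logistic model secures neither and admits covariates recorded after the endpoint

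*Combined protocol and SAP*

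**What the plan says.** The primary comparison in section 10.4.3 is unadjusted: "The comparison of binary endpoints (B-lines < 15) will be performed using Chi-square or Fishers exact test, as appropriate". The endpoint is read when the patient leaves the ED or at a "maximum of 6 hours after enrollment, whichever comes first" (section 4.2.1).

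Two pre-randomisation variables are in hand for every patient. The T00 scan decides eligibility: "Clinical diagnosis of AHF and presence of > 15 total bilateral B-lines distributed in at least 4 zones on initial LUS" (section 5.1; timing in section 7.3.7). Site defines the randomisation tables, with blocks of 2, 4 and 6 (section 10.6.1).

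Section 10.4.3 adds a logistic model intended to gain precision. Its open candidate list includes "in-hospital medications, baseline renal function, serum sodium, natriuretic peptide levels, troponin levels, renal function, baseline blood pressure, and discharge medications". Hemoconcentration may also enter, defined so that "any increase in value in both hematocrit and hemoglobin during hospitalization will be considered positive". Neither T00 nor site is named. Selection is data-driven: "Covariates with univariately significant association with the outcome will be included together with the treatment indicator in a logistic regression model". Size is capped: "we will limit the number of covariates (including treatment indicator) such that there is 10 events per covariate".

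For the exploratory days-alive-and-out-of-hospital endpoint, section 10.4.4 reasons differently: "The PO regression allows for adjustment of baseline covariates to enhance power".

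**The concern.** The endpoint is a B-line count reaching a fixed cut-off, so the starting count is a plausible predictor of who reaches it. Planned power is only 81%. If T00 is prognostic, adjusting for it raises power and removes chance baseline imbalance from the estimate, at no cost in data. The plan accepts this reasoning for an exploratory endpoint but not for the primary one.

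The supplementary model does not fill the gap. A significance screen in about 118 evaluable patients will often drop a useful covariate, and the final model is not known until the data are seen. The list also mixes baseline variables with ones that can be consequences of treatment or of the endpoint itself. Conditioning on those changes what the treatment coefficient means.

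**Working it through.** **1. The plan's own figure.** Inputs from section 10.5: 59 per arm, 25% against 50%, two-sided 0.05. With pooled variance under the null, the mean rate is 0.375 and

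z = [0.25 × √59 − 1.960 × √(2 × 0.375 × 0.625)] / √(0.25 × 0.75 + 0.50 × 0.50) = (1.920 − 1.342) / 0.661 = 0.874, so power = 0.809.

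Exact enumeration also gives 0.809 for the uncorrected chi-square (0.754 for Fisher). The chi-square's exact type I error at a common 25% rate is 0.052. The stated 81% stands.

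**2. Timing of the covariates against an endpoint at 6 hours or earlier.**

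| Variable | When known | Section |
|---|---|---|
| T00 count | before randomisation | 5.1, 7.3.7 |
| Site | at randomisation | 10.6.1 |
| In-hospital medications | after randomisation | 10.4.3 |
| Discharge medications | after the endpoint | 10.4.3 |
| Rise in hematocrit and hemoglobin | over the hospital stay | 10.4.3 |
| NT-proBNP change | second central sample at day 7 or discharge | 10.4.3, 7.3.7 |

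**3. Power gain when r is equal in both arms.** Here r is the within-arm, within-site correlation of log T00 with log final count. It is assumed, as are the between-site SD (on the latent outcome scale) and truncation of T00 at −1 SD to represent the entry cut-off. The simulation had 118 patients, blocks of 2/4/6 within 3 or 4 site strata, and 5,000 replicates per cell. The adjusted analysis is logistic regression conditional on site, with treatment and log T00, tested by Wald.

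| r | Gain over chi-square, points (site SD 0 to 0.3) |
|---|---|
| 0 | −0.8 to +0.2 |
| 0.3 | +1.0 to +1.7 |
| 0.5 | +4.7 to +4.9 |

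For example, with 3 strata and no site spread, power goes from 0.807 to 0.856 at r = 0.5. Null rejection was 4.1–5.3% in all 24 cells. Site alone adds −0.1 to +0.3 points at SD 0, +0.5 to +1.4 at SD 0.3, and +2.4 to +4.2 only at SD 0.6.

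**4. Power gain when r is weaker in the LUS arm.** Treatment in that arm is driven by the count until it reaches the target (sections 4.1 and 6.1.1), so high starters may be treated for longer and the T00/outcome link may weaken. Simulation without site effects, 4,000 trials, Monte Carlo error 0.2–0.4 points:

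| r, usual care / LUS | Gain, points |
|---|---|
| 0.3 / 0 | −0.1 |
| 0.3 / 0.1 | +0.9 |
| 0.5 / 0 | +1.3 |
| 0.5 / 0.2 | +2.5 |

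**5. Chance imbalance.** The SE of the T00 difference between arms is √(2/59) = 0.184 SD, so an imbalance of 0.3 SD or more (0.3/0.184 = 1.63 SE) occurs in about 10% of trials. With equal r it moves the unadjusted risk difference by about 3 points at r = 0.3 and 4–6 at r = 0.5.

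**6. The significance screen.** Even if T00 were a candidate, p < 0.05 would drop it in 34–47% of trials at r = 0.3. Site would be dropped in about 67% at SD 0.3.

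**7. A post-endpoint covariate in the supplementary model.** A binary marker with an assumed correlation with the final count, entered by the plan's rule (8,000 replicates, r = 0.3, no site spread), against 80% for logistic regression on treatment alone:

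| Correlation | Kept in | Power |
|---|---|---|
| 0.2 | 28% | 79% |
| 0.3 | 54% | 78% |
| 0.5 | 95% | 70% |
| 0.7 | 100% | 57% |

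**8. Events per term.** Expected events are 59 × 0.25 + 59 × 0.50 = 44.25 at design rates and 59 × 0.50 = 29.5 with no effect.
- Conditional model, 2 estimated terms: 22.1 and 14.8 per term, within the plan's rule.
- Unconditional model with site indicators, 4 sites, 5 terms: 8.9 and 5.9.
- The same with 3 sites, 4 terms: 11.1 and 7.4.

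**The case against.** The strongest reply is that nothing in the primary analysis is broken. Randomisation protects the comparison, section 10.4.2 tabulates baseline imbalance, and an adjusted model is already planned. The gain rests on a correlation that the documents do not contain, and step 4 shows it can nearly vanish. All of that stands. It limits the primary-test part to an efficiency gain; it does not make adjustment harmful, since the worst simulated loss is 0.8 points.

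It also stands that the post-endpoint covariates sit in a supplementary model, that hemoconcentration is only optional there, and that the harm is 1–2 points of power at correlations of 0.2–0.3. The larger losses need stronger assumed correlations.

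A reader might infer more:
- **That the primary test is invalid or the trial underpowered for its stated effect.** It is not: size and power both check.
- **That post-endpoint covariates bias the primary result.** They cannot, because the primary p-value comes from the unadjusted test.
- **That about ten points of power are on offer.** The simulation gives +9.2 to +10.5 at r = 0.7 in both arms, but the documents support neither so strong a correlation nor its equality across arms.

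**Conclusion.** The point holds as a missed, nearly free improvement in the primary analysis and a poorly specified supplementary model. It is not an error in the primary test or the sample size. The supplementary-model part needs no assumption about r: the listed variables postdate randomisation, two of them postdate the endpoint, and the selection rule is data-dependent.

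The efficiency part does depend on r. Expect about 0 at r = 0, +1 to +2 points at r = 0.3 and +5 at r = 0.5 if r is equal across arms, and about 0 to +1 and +1 to +2.5 if it is weaker in the LUS arm. Site contributes at most about 1.4 points unless sites differ strongly. If r describes unselected patients, the assumed −1 SD truncation shrinks 0.3 and 0.5 to 0.24 and 0.42, and the equal-arm gains to +0.3 to +1.5 and +2.8 to +4.3. The only ED spread given (78 ± 47, section 2.2, 28-sector scoring) would put 15 lines near −2.7 SD if log-normal, but the trial uses 8 zones, so the true truncation is unknown.

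**What to change.** 1. **Primary model.** Pre-specify logistic regression conditional on randomisation site, one stratum per randomisation table, with treatment and log(T00 count + 1), tested by Wald. Keep the chi-square as supportive. Conditioning works with 3 or 4 tables, which matters because the Protocol Summary gives three sites (four hospitals) and section 10.2 gives four. The +1 is needed because a blinded Core Lab re-read could be 0. The simulations used the plain log, which differs little above 15 lines (ln 16 = 2.77, ln 17 = 2.83).
2. **Definitions first.** State whether T00 is the bedside or the Core Lab reading. Settle the per-sector maximum (20 in section 17.1, 10 in section 17.3) and the cut-off (15 or fewer in section 4.2.1, fewer than 15 in section 10.4.3).
3. **Effect measure.** Report a standardised risk difference with 95% CI beside the conditional odds ratio. Either exempt its unconditional model from the 10-events rule as pre-specified, stating the counts in step 8, or standardise over treatment and T00 only.
4. **Supplementary model.** Use only pre-randomisation covariates named in advance. Drop the univariate screen, in-hospital and discharge medications, in-hospital hemoconcentration and any NT-proBNP change.
5. **Timing.** Date the amendment before database lock and release of Core Lab reads (section 17.3), and have it made by people who have not seen interim data by arm.

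**Cost:** one SAP amendment and a few lines of SAS (PROC LOGISTIC with a STRATA statement); no new data. **Downsides:** the odds ratio is conditional; the test and the risk difference may come from different models; simulated coverage of the risk-difference CI (site-indicator model, influence-function SE) was 93.6–95.3%; and nothing is gained if T00 is not prognostic and sites do not differ. Because the trial is unblinded and staff count B-lines at the bedside, independence from outcome data rests on the amendment date and the withheld Core Lab reads.

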### 7.3.7 SCHEDULE OF EVENTS TABLE

Schedule of Events	Screening	Day 1 T00	Day 1 T02-04	Day 1 T06	Day 2-6 T24-D6	Day 7 or D/C*	30 & 90 day follow up	Quarterly
Informed consent (I/E)	X							
Medical History	X							
Medication history	X							
Clinical Assessment #		X	X	X	X	X		
Body Weight, height, Vital Signs	ED SOC	VS only	VS only	VS only	BW/VS only	BW/VS only		
Labs: Electrolytes, hematology, NP, eGFR, Troponin	ED SOC							
NT-proBNP / hsTroponin (for central lab processing)		X				X		
12-lead ECG	ED SOC							
CXR	ED SOC							
LUS B-lines 8 zone	X (LUS T00)		X	X	X	X		
LUS Guided AHF Management or Usual Care		X	X	X				
Lab draw: eGFR, Hgb/Hct ^		X				X*		
Prep and Storage of Samples		X				X		
eCRF/data collection/verification		X					X	

Assessment of AE/SAE's							X	
Phone follow-up Vital Status							X	
Batch shipment of samples								X
Subject payment		X					X	

SOC = standard of care, ED = Emergency Department, I/E = inclusion, exclusion, CV = cardiovascular, LUS = lung ultrasound, BW = body weight, NP = natriuretic peptide ^if collected as part of standard of care, will use that result. The last collected result will be used if not drawn on or close to discharge \*Day 7 or discharge, whichever comes first. #As documented by clinician during inpatient stay or per form for ED phase

Further detail regarding timing of assessments: [NOTE: given clinical circumstances (i.e. left the ER for a test, discussion with consultant, etc) – the SITE PI has final discretion to continue to image a patient before or after the allotted window. This time MUST be recorded in the eCRF]

- T00: initial LUS scan (in ED for screening and eligibility)
- T02: 2-4 hours after initial treatment (in ED) (+/- 30 minutes)
- T06: 2-4 hours after T02 or pre-ED discharge, whichever comes first (+/- 60 minutes)
- HD2: 24 hours after initial scan (Day 2) (+/- 6 hours)
- HD3: 48 hours after initial scan (Day 3) (+/- 8 hours)
- HD4: Day 4 (anytime during day)
- HD5: Day 5 (anytime during day)
- HD6: Day 6 (anytime during day)
- HD7: Day 7 (anytime during day)

\* NTproBNP/hsTnT blood draw. This should occur within 6 hours of randomization. Ideally, the blood draw should occur as soon as possible after randomization, preferably within 3 hours.

\*\* For vital signs during hospitalization. The nearest vital signs to the LUS exam will be captured.

^HD = Hospital day

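### The supportive logistic model for the primary endpoint may adjust for variables not fixed before randomization, so its treatment odds ratio can be biased in either direction

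*Combined protocol and SAP*

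**What the plan says.** The main comparison in section 10.4.3 is an unadjusted chi-square or Fisher's exact test. The section then adds: "Potential covariates will also be considered in a logistic regression setting to improve precision". The candidates start with baseline co-morbidities and medications and continue with "in-hospital medications, baseline renal function, serum sodium, natriuretic peptide levels, troponin levels, renal function, baseline blood pressure, and discharge medications". Physical exam, other vital signs and hemoconcentration may also be included; for the last, "any increase in value in both hematocrit and hemoglobin during hospitalization will be considered positive".

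The selection rule is: "Covariates with univariately significant association with the outcome will be included together with the treatment indicator in a logistic regression model". The number of terms, treatment included, is capped at one per ten events.

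The endpoint in section 4.2.1 is read when ED management ends or at a "maximum of 6 hours after enrollment, whichever comes first". In the section 7.3.7 schedule the row "Lab draw: eGFR, Hgb/Hct" is marked at T00 and then only at the last inpatient time point, "Day 7 or discharge, whichever comes first". The row "Labs: Electrolytes, hematology, NP, eGFR, Troponin" is marked at screening.

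Section 10.4.4 speaks of baseline covariates, but only for the days-alive-and-out-of-hospital model. Nothing in section 10.4.3 sets that limit for the primary endpoint.

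**The concern.** Adjustment sharpens a randomized comparison when the covariates are fixed before randomization. A variable that treatment can change, or that is measured after the outcome, does not have that property. Conditioning on it can remove part of the effect under study, or open a path between arm and prognosis that randomization had closed.

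The list mixes both kinds. It attaches the word baseline to co-morbidities, medications, one renal function entry and blood pressure, and omits it elsewhere, so a general baseline limit cannot simply be read in. Univariate screening gives no protection, because a variable on the treatment pathway, or one that reflects the outcome, is likely to be associated with the outcome.

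At stake is the adjusted odds ratio of a pilot whose stated purpose (section 3) is to inform a definitive trial. It could disagree with the main test because of which covariates entered, and be misread as a weaker or stronger strategy effect.

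**Working it through.** **Timing of the candidates against an endpoint at 6 hours or less**

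| Candidate | When known |
|---|---|
| Baseline co-morbidities, medications, renal function, blood pressure | Before randomization: sound |
| Sodium, peptide, troponin (undated) | Sound if taken from screening labs (7.3.1, 7.3.7). The central peptide and troponin draw is allowed up to 6 hours after randomization |
| Renal function, second entry (undated) | T00, or day 7/discharge |
| In-hospital medications | After randomization. Inpatient drugs mostly follow the endpoint; any diuretic given within 6 hours is partly set by arm, because for patients already given furosemide section 6.1.1 makes further diuretic differ by arm |
| Hemoconcentration during the stay; discharge medications | Generally after the endpoint |

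**Plan's own figures.** Inputs from section 10.5: 59 per arm, 25% vs 50%, two-sided 0.05. Exact enumeration of the uncorrected chi-square test gives 80.9%, matching the stated 81%. The true odds ratio is (0.50/0.50)/(0.25/0.75) = 3.0. Expected events are 59 × 0.25 + 59 × 0.50 = 44.25, so 4 terms. If both arms are at 25%, 118 × 0.25 = 29.5 events, so 2 terms.

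**Illustration A: ED diuretic dose as the candidate.** The documents give no mediation share, dose difference or correlations, so all are assumed. A is arm, S is severity, and D is dose:

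- D = k·A + ρ·S + √(1−ρ²)·e
- Y* = z(0.25) + (1−m)·0.674·A + (m·0.674/k)·D − g·S + error, within-arm variance 1; response if Y* > 0

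Here 0.674 = z(0.50) − z(0.25), m is the share of the effect carried by dose, k the dose shift in SD and g the severity strength. D is kept only if its univariate p < 0.05; otherwise the model holds treatment alone. Results for k = 1, g = 0.6:

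| m | ρ | D enters | Median OR | Treatment p < 0.05 (unadjusted 80–81%) |
|---|---|---|---|---|
| 0.50 | 0 | 97% | 1.8 | 27–28% |
| 0.25 | 0 | 71% | 2.4 | 53–55% |
| 0.50 | 0.5 | 34% | 2.8 | 72% |
| 0.25 | 0.5 | 6% | 3.1 | 81% |

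With m = 0 and ρ = 0.7, the median OR rises to about 4.6. At equal dose the LUS-arm patients are then the less severe ones, which inflates the odds ratio.

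With no true effect (Y* = z(0.25) − g·S + error; k 0.5 or 1, g 0.4 or 0.6), the false-positive rate is about 5–6% at ρ = 0.3, 6–14% at 0.5 and 7–32% at 0.7, against about 5% unadjusted. In the 32% cell the median OR is about 2.1 where the truth is 1.0.

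**Illustration B: a yes/no marker clearly after the outcome** (30–50% positive, latent correlation r with the 6-hour response):

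| r | Enters | Median OR | Treatment p < 0.05 |
|---|---|---|---|
| 0.3 | 52–55% | 3.0 | about 79% |
| 0.5 | 94–95% | 2.9 | about 73% |
| 0.7 | 100% | 2.7 | about 60% |

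**Check of the alternative: treatment plus T00 count.** At latent correlation 0.1/0.3 with the response, power is 81.8/82.9% against 80.9/80.2% unadjusted, a gain of 0.9/2.7 points. Type I error over correlations 0 to 0.5 is 5.2–6.0%. The conditional OR at correlation 0.3/0.5 is 3.2/3.7.

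**The case against.** The wording is permissive (candidates are considered, some may be included), the main test is untouched, and several candidates are proper baseline variables. All of that stands, and it limits the point to a supportive analysis.

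The large figures depend on reading in-hospital medications as ED diuretic dose. Table 3 in section 4.2.2 lists ED treatment and hospital treatment separately, so inpatient drugs are the more natural meaning. This also stands, although sections 6.1.1 and 6.1.2 let the protocol continue on the floor up to 6 hours, so some overlap remains. For variables clearly after the outcome, Illustration B shows little bias and mainly a loss of power.

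The simulation has further limits. No document supports a 1 SD dose difference; section 6.1 has usual care follow the treatment protocol too, unless the clinician judges no further treatment is warranted. Dosing in the LUS arm responds to persisting B-lines, and a rough run with such feedback gave a median OR of 3.2–3.3, with no shrinkage. Only one candidate was simulated, whereas the real list competes for about three places besides treatment. These objections stand against any single figure. They do not supply a limit to pre-randomization values, which the text lacks.

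A reader might infer that the model would shrink the treatment effect. The documents do not support a direction: the cells above go both ways. A reader might also take the rise in the standard error of the log odds ratio, from 0.40 to 0.45 when dose enters, as lost precision. It is not evidence of that, because a sound baseline covariate produces the same rise.

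**Conclusion.** The point holds for the supportive logistic model only. As written, section 10.4.3 lets it condition on variables affected by treatment or known after the endpoint, and the univariate screen does not keep them out. The adjusted odds ratio can be biased either way and can disagree with the main test. Against a true 3.0, assumed inputs gave medians from about 1.8 to about 4.6, with some cells showing almost no bias. The false-positive rate ranged from about 5% to 32%, and the top figure needs a 1 SD shift, strong severity and a correlation of 0.7 together. These are illustrations, not estimates. Confidence is high on the text and low on size.

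It would be wrong to infer that the primary result is compromised: the unadjusted test, its 81% power and N = 130 do not depend on this model. The correction is still worth making before outcomes are seen.

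**What to change.** In section 10.4.3, replace the open candidate list and the univariate screen with one pre-specified model, labelled supportive to the unadjusted full-analysis-set test and limited to values fixed before randomization. An example is treatment plus T00 total B-line count, counted on the same scale as the endpoint. That is 2 terms, within the plan's events rule even at about 30 events. Site is optional: three sites make 1 + 1 + 2 = 4 terms, the cap at 44 events; four hospitals make 5, so use strata in that case. Allow peptide, troponin, sodium or renal function only from pre-randomization samples such as the local screening labs.

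Move in-hospital and discharge medications, later renal function and hemoconcentration to exploratory association analyses; NT-proBNP change is already described as one. State that the adjusted odds ratio is conditional and not directly comparable with the unadjusted one.

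The cost is wording only, since the T00 count, screening labs and site are already collected. The downside is an adjusted odds ratio that differs from the unadjusted one even without bias. The expected power gain is small, about 1 to 3 points at T00 correlations of 0.1 to 0.3, so the main gain is freedom from bias.
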